8.5 Database lock and exports

At the point of data lock all user access to the database will be changed to read-only to prevent any changes to the data. A final data extract will be produced for analysis and a copy archived with restricted access.

8.6 Database archiving

The database export created at the point of database lock will be stored on secure UoB servers for the duration of the archive period. The REDCap database will then be archived following REDCap standard procedures. The BTC systems team have protocols in place to retrieve the database from archive for inspection purposes, if required.

8.7 Data sharing

Members of the TMG will develop a data sharing policy consistent with UoB policy.

All data sharing will comply with the consent provided by participants and adheres to data protection legislation.

A data sharing plan will be developed at the outset of the trial. This will describe who will have access to the full dataset, and the process of requesting access to the full dataset.

9 RISK REVIEW AND MONITORING

The trial will be monitored and audited in accordance with the Sponsor's policy, which is consistent with the UK Policy Framework for Health and Social Care Research. All trial related documents will be made available on request for monitoring and audit by the Sponsor, the relevant REC and for inspection by regulatory authorities.

9.1 Risk Assessment

The risk assessment process is a careful examination of what could cause harm, who/what could be harmed and how, and risks to the study integrity. Reasonably foreseeable risks associated with a research study, and actions to control the risks so far as is reasonably practicable, will be identified and documented as soon as possible in a study specific risk assessment.

The risk assessment documentation and any subsequent revisions should be kept in the TMF. The risk assessment should be an ongoing process. Each time there are changes to the perceived risks and mitigating circumstances these must be agreed by the TMG and CI and documented.

9.2 Monitoring

Monitoring is defined as the act of overseeing the progress of a clinical trial, and of ensuring that it is conducted, recorded, and reported in accordance with the protocol, SOPs, GCP, and the applicable regulatory requirements.

The purpose of monitoring is to verify that:

- The rights and well-being of the participants are protected;
- The reported study data are accurate, complete and verifiable from source documents;
- The conduct of the study complies with the currently approved protocol, GCP and the applicable regulatory requirements.

Study monitoring activities should be identified based on the study-specific risk assessment and will be documented in a Monitoring Plan. This will be developed in consultation with the Sponsor based on the trial risk assessment.

9.3 Monitoring of study by Sponsor

The trial will be monitored and audited in accordance with the Sponsor's policy, which is consistent with the UK Policy Framework for Health and Social Care Research. All trial related documents will be made available on request for monitoring and audit by the Sponsor (or BTC if they have been delegated to monitor) and the relevant REC.

University Hospitals Bristol and Weston NHS Foundation Trust (UHBW) may be used to externally monitor the trial on behalf of the Sponsor.

9.4 Monitoring of study by BTC

The Sponsor usually delegates some monitoring activities to the central trial team at BTC. Checks of the following would be typical:

- Informed Consent process and documentation
- Inclusion and Exclusion criteria verification
- Completed source documents and CRFs, data completeness and other types of data queries
- Study procedures and / or intervention compliance
- Safety documentation and adverse event reporting
- Protocol deviations

The BTC will carry out regular central monitoring and audit of compliance of centres with Good Clinical Practice (GCP) and trial-specific data collection procedures described in the protocol. The trial database will have in-built validation and the TMG will review the completeness of the data throughout the trial. The BTC will not check CRFs or other source data against the data entered to the trial database, unless there are good reasons to visit a centre to complete a monitoring visit (e.g. the central monitoring highlights a problem).

The quality of the study data may be monitored through centralised database monitoring. Validation checks are documented in the database specification document. Data completeness and accuracy checks may be run through the study databases. Data queries are usually reported via the study database and may be supplemented by additional independent data checks carried out by the study statistical team.

Other study monitoring activities may also be carried out, e.g. remote centre monitoring, on site (centre) monitoring.

The plan will include elements of self-monitoring at centres (e.g. checking of site file documentation, safety reporting, and consent form reviews) and database checking and source data verification (SDV) checks. The results of self-monitoring will be shared with the CI/PI and Sponsor as appropriate. Areas of concern will be followed up and this may involve a site visit.

9.5 Training of recruiting sites and GP practices

Initiation training

Before the trial commences at each participating centre, training will be organised by Bristol Trials Centre (BTC). The training provided will ensure that site research personnel fully understand the protocol, case report forms (CRFs) and the practical procedures (working instructions) for the trial including using the data capture systems. These sessions may be provided virtually or on-site. They may include training videos and manuals as well as a site initiation meeting. Initial training and any subsequent training e.g. for new staff members will be documented.

Training for GP practices will also be organised by Bristol Trial Centre, ensuring that site staff fully understand the screening criteria, referral procedure, and the record search and Docmail processes for mail outs.

Each GP practice recruiting to the trial will receive information and advice on all trial recruitment procedures prior to the start of recruitment. This will be provided to collaborating Bristol practices by the Trial Manager, with the assistance of other members of the trial team as appropriate. Guidance will be provided to London and Exeter centre GP practices by the local trial team with assistance

from the Bristol centre as required. A training log will be maintained within the Trial Master File (TMF). Participating centres will be informed of amendments by the Bristol Trials Centre, who will pass this information on to GP practices as required.

Investigators' responsibilities

Investigators must ensure that local research approvals have been obtained and any required contractual agreements have been signed off by all parties before recruiting any participants. Investigators will be required to ensure compliance to the protocol and completion of the CRFs. Investigators will be required to allow access to trial documentation or source data on request for monitoring visits and audits performed by the Sponsor, BTC or any regulatory authorities.

Investigators will be required to read, acknowledge and inform their team of any amendments to the trial documents approved by the HRA/REC that they receive and ensure that the changes are complied with.

9.6 Protocol compliance

Prospective, planned deviations or waivers to the protocol are not allowed. Accidental protocol deviations will be documented and reported to the CI and Sponsor in line with the Sponsor's reporting requirements. They will also be reported to the DMC. In the event of systematic protocol deviations, investigation and remedial action will be taken in liaison with the CI, DMC and the TMG.

Sponsor specific procedures will be followed for the reporting of any breaches. All protocol breaches will be reported to the Sponsor as soon as possible after they occur/are identified. The Sponsor will determine whether it constitutes a serious breach, requiring onward reporting to the REC.

9.7 Serious Breaches to GCP and/or the protocol

A "serious breach" is a breach which is likely to affect to a significant degree:

- a. the safety or physical or mental integrity of the subjects of the trial; or
- b. the scientific value of the trial.

In the event that a serious breach is suspected, the Sponsor will be notified as soon as possible and within 24 hours of becoming aware of the event. The serious breach will be reviewed by the Sponsor in collaboration with the CI. The Sponsor will determine whether it constitutes a serious breach, requiring onward reporting to the REC. If appropriate, the Sponsor will report it to the REC and the relevant NHS host organisation within seven calendar days of become aware of the serious breach.

Reports of misconduct or malpractice will be dealt with according to the University of Bristol's Regulations on Research Misconduct, Preventing harm in research (safeguarding) and Whistleblowing policies. These policies can be found on the University of Bristol website.

10 ANALYSES

10.1 Statistical analysis

Analyses will be directed by a pre-specified Statistical Analysis Plan (SAP) and will be in line with CONSORT reporting guidelines for clinical trials. The SAP will be prepared and approval sought from the TSC prior to database lock. The analysis plan will be published on the University of Bristol Research Portal. All analyses (unless otherwise stated) will be conducted on an intention to treat

(ITT) basis. Continuous data will be summarised as mean and SD or median and inter-quartile range (IQR) if distributions are skewed. Categorical data will be summarised as number and percentages.

10.1.1 Efficacy Analysis

In the primary efficacy analyses, we will compare groups 'as randomised' using linear regression adjusting for stratification/minimisation variables and baseline measurement of the outcome (BDI-II score).

Secondary analyses will adjust for any substantial baseline imbalances in key prognostic factors based on descriptive statistics. Impact of process measures (e.g. involvement in EMDR/other interventions) will be explored. Repeated measures analyses will incorporate outcomes over 52 weeks. An interaction between treatment group and time will formally assess whether effects are sustained or emerge later. A Complier Average Causal Effect (CACE) analysis is planned to estimate the treatment effect among compliers who attend an adequate number of EMDR sessions (defined as ≥9 sessions by 26 weeks). We will explore any potential therapist effects using a fully heteroscedastic mode [68]I. Sensitivity analyses will examine impact of missing data. A priori subgroup analyses will explore possible differential treatment effects based on baseline depression chronicity and severity by including an interaction term between treatment allocation and each factor.

Model validity will be checked using standard methods; if a model is a poor fit, alternative models or transformations will be explored.

10.1.2 Mechanistic analysis

To determine whether reductions in depressive symptoms are mediated via the proposed mechanisms (vividness and emotional intensity of depression-related memories, negative self-beliefs and symptoms of re-living, avoidance and hyper-arousal), we will use a cutting-edge counterfactual framework based on the parametric g-formula [69]. This can accommodate both continuous (e.g., depressive symptoms, BDI-II score) and binary outcomes (e.g., remission), multiple mediators, and potential intermediate confounders (e.g., depressive symptoms during therapy). With continuous outcomes, we will also use traditional mediation (products of coefficients within a structural equation modelling (SEM) framework) to compare results with the counterfactual approach, and estimate the path specific effects via each mediator.

We will identify potential baseline/intermediate confounders using Directed Acyclic Graphs. Despite the exposure being randomised, there may still be mediator-outcome confounders (e.g. prognostic factors, baseline measures of the mediators and outcome) which will be measured and included. We will compare findings using other methods making different assumptions to strengthen causal inference (e.g., instrumental variable (IV) methods which address mediator-outcome confounding and measurement error in the mediators through identifying covariates which moderate the effect of treatment on the mediators [70, 71]). If strong moderators of the effect of treatment on the mediators cannot be identified to use as an IV, we will examine the sensitivity of the results to the assumption of no unmeasured mediator-outcome confounders [72-74]. Finally, we will decompose CACE into the complier average natural direct effect and the complier average causal mediated effect via each of the proposed mechanisms using IV SEM [75]. This will allow us to examine the role of treatment receipt (e.g. attending an adequate number of EMDR sessions) on the outcome (e.g. depressive symptoms) via the mediators using randomisation as an IV.

If the WM hypothesis is correct, then EMDR will be more effective in those with lower WM capacity. So, we predict a negative relationship between WM capacity and baseline to post-treatment symptom reduction in the EMDR group. We will report a two-tailed correlation between baseline

WM capacity (three continuous measures) and change in depressive symptoms on the BDI-II between baseline and 26 weeks. We will also explore associations using suitable regression models and undertake exploratory analyses testing for an interaction between baseline WM (for each of the three measures) and treatment allocation. Analysing each of the three measures of WM separately will help us understand which aspects of WM are important. Tests for interaction will be interpreted with caution given that they will be underpowered.

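### The sensitivity analysis for unmeasured mediator-outcome confounding is promised only as a fallback to a moderator-based IV; it should be run in every case

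*Protocol*

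**What the plan says.** Section 4.4.1 makes mediation by three groups of 16-week measures the primary mechanistic objective. Section 10.1.2 estimates it with the parametric g-formula and uses product-of-coefficients SEM as a comparison for continuous outcomes.

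On confounding of mediator and outcome, section 10.1.2 sets out four steps:

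- Measured confounders are adjusted for: "there may still be mediator-outcome confounders (e.g. prognostic factors, baseline measures of the mediators and outcome) which will be measured and included".
- Results are set against other approaches: "We will compare findings using other methods making different assumptions to strengthen causal inference". The example given is an IV analysis whose instruments come from covariates that modify how strongly EMDR changes each mediator. It is aimed at confounding between mediator and outcome and at error in measuring the mediators.
- A sensitivity analysis follows on a condition: "If strong moderators of the effect of treatment on the mediators cannot be identified to use as an IV, we will examine the sensitivity". What would then be examined is how far the findings depend on mediator and outcome having no unmeasured common cause, by the methods cited as references 72-74.
- A complier-average decomposition is planned in any case, "via the mediators using randomisation as an IV".

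The protocol does not say what makes a moderator strong, and it lists no candidate moderators.

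**The concern.** The condition ties the sensitivity analysis to the wrong event. Whether a covariate moderates the effect of EMDR on a mediator tells us nothing about whether mediator and outcome share an unmeasured cause. The g-formula and product-of-coefficients estimates need that assumption equally in both branches, yet the plan commits to probing it in only one.

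The other unconditional steps do not fill the gap. SEM by product of coefficients makes the same assumption. Adjusting for measured confounders cannot deal with unmeasured ones. The complier-average step uses randomisation as the instrument for treatment receipt, not for the mediator.

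At stake is the primary mechanistic conclusion. It could be reported with an imprecise IV comparison and without any statement of how much unmeasured confounding would remove the indirect effect.

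**Working it through.** **Inputs.** From section 6.6.2: N = 285 after 25% attrition; total effect 0.378 SD; exposure-mediator effect √0.13 = 0.361 SD; confounding correlation 0.3. From section 6.5: 1:1 allocation. Assumed here: two-sided 5% for the mediation tests (6.6.2 gives no alpha), residual SDs near 1, and the thresholds and numbers of candidate moderators, which the protocol does not give.

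**1. The plan's own figures reproduce.** For a joint test of both paths:
- Path a: z = 0.361 × 0.5 × √285 / √(1 − 0.13/4) = 3.09, so power = Φ(3.09 − 1.96) = 0.872.
- Path b: slope b = share × 0.378 / 0.361, which is 0.419, 0.315 and 0.210 for shares of 40%, 30% and 20%. Then z = b × √[285 × (1 − 0.09 − 0.0325)], giving power of 1.000, 0.999 and 0.912.
- Joint power: 87.2%, 87.1% and 79.5%, against the stated 87.2%, 87% and 79.4%.

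**2. How large an interaction an F of 10 needs.** With 1:1 arms, F ≈ N × ¼ × Var(X) × g², where g is the interaction.
- Continuous covariate, Var(X) = 1: g = 2√10/√285 = 0.375 SD per SD.
- Balanced binary covariate, Var(X) = ¼: g = 4√10/√285 = 0.749 SD.

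Both are at least as large as the 0.361 SD average effect on the mediator. By the noncentral F distribution, a true interaction of 0.2 SD per SD passes F>10 in 7% of trials, one of 0.36 in 45%, and one of 0.5 in 85%.

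**3. Precision if F = 10 is just reached.** The standard error of the IV slope is about (residual SD of outcome ÷ residual SD of mediator)/√F = 1/√10 = 0.316. The 95% half-width is 1.96 × 0.316 = 0.62, about twice the slope of 0.315 that corresponds to 30% mediation.

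**4. Chance that a null moderator looks strong.** For k independent null candidates this is 1 − (1 − p)^k, with p = 0.0017 for F>10:

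| k | p<0.05 | p<0.01 | F>10 |
|---|---|---|---|
| 5 | 23% | 4.9% | 0.9% |
| 10 | 40% | 9.6% | 1.7% |
| 20 | 64% | 18% | 3.4% |

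**5. What the IV returns in those trials.** The check was a simulation of 6,000 trials per setting, with N = 285, no true moderators, and a shared cause that biases the mediator-outcome slope by 0.30. The best of 10 or 20 covariates served as the instrument.
- True slope 0, p<0.05: median IV estimate 0.30-0.31, against 0.30 for ordinary regression.
- True slope 0, F>10: median 0.28-0.37, with 95% interval coverage of 78-82%.
- True slope 0.315, F>10: median 0.60-0.67, against 0.61 for ordinary regression, with coverage of 83-85%.

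The F>10 rows rest on only 118 to 206 passing trials each, so their medians are approximate. The direction is clear: a chance instrument reproduces the confounded answer.

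**The case against.** Four points in the plan's favour carry weight.

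- **The IV is itself a check.** A reader might infer that finding a moderator cancels the only safeguard against this bias. The documents do not support that. The moderator-IV is aimed at mediator-outcome confounding, it is one example in an open list, and it is what runs when a moderator is found. Nor does the text forbid the sensitivity analysis in that branch; it simply makes no commitment to it.
- **The selection rule is not stated.** A reader might infer that moderators will be picked by observed strength in the trial's own data. Section 10.1.2 speaks only of "through identifying covariates which moderate the effect of treatment on the mediators". The candidate list and the meaning of strong can properly sit in the SAP, which is not at hand.
- **The caution about power is about something else.** "Tests for interaction will be interpreted with caution given that they will be underpowered" refers to working memory by treatment allocation, not to moderators of the effect on the mediators. It is not an admission about the IV.
- **The chance route is rare at a conventional threshold.** It is about 1-2% at F>10 with 5-10 null candidates. The IV interval would also be wide. In a simulation with a true slope of 0.20 and a confounded estimate of about 0.50, it still included zero in 55-71% of the trials that passed F>10, so a convincing false confirmation is not the typical result.

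A bias analysis as the fallback when no instrument exists is a sensible instinct. None of these points gives a reason to leave it out when an instrument is found: the g-formula estimate still rests on the same assumption.

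**Conclusion.** The point holds as a flaw in how the protocol fixes the sequence of analyses. Two complementary checks are written as alternatives, and the one that directly probes the assumption behind the main mediation estimate is promised in only one branch. This follows from the wording of section 10.1.2 and does not depend on any simulation.

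The figures show why the IV is a poor substitute. It needs an interaction at least as large as the assumed average effect on the mediator, and at F = 10 its interval is about ±0.62. In the uncommon case of a chance pass, it leans towards the confounded value. The rate of chance passes depends on an assumed threshold and number of candidates, so it should be read as a range: about 1-2% at F>10 with 5-10 candidates, and 23-40% for the same numbers at p<0.05.

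Severity is minor to moderate. The point touches the mechanistic conclusion only; the efficacy result, the sample size and the stated power stand.

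**What to change.** In section 10.1.2, delete the condition about failing to identify strong moderators. State that the sensitivity analyses already cited there (references 72-74) will be run for every primary mediator in all cases and reported beside the g-formula estimate. Add that any moderator-based IV result is supportive.

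Naming the candidate moderators and reporting the first-stage F are worth doing but belong in the SAP.

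The cost is one sentence in the protocol and a little more analysis, with no new data. The downside is that the mediation result will always be shown together with its fragility.

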4.4.2 Secondary mechanistic objective

To determine whether baseline working memory capacity is associated with treatment response at 26 weeks.

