5.8.4 Target sample size (with calculation/justification)

The established minimum clinically important difference (MCID) for BDI-II is a 23% reduction ([49]). Assuming a mean BDI-II at follow-up in usual care of 22.0/24.5 (SD 13.5/13.1)([30],[47]), this translates to 5.1-5.6 BDI-II points or an effect size of 0.378 (based on a standard deviation of 13.5). 149 are therefore needed per group for 90% power at the 2-sided 5% significance level. 380 participants will be recruited, allowing, conservatively, for a correlation of 0.20 between baseline and 6-month BDI-II scores and 25% attrition at 26 weeks (based on our past experience & our recent NIHR funded INTERACT trial (ISRCTN13112900 [44]). Early contact with the participants will maximise retention (as advised by PPI) and we will use guidance to help retain individuals from diverse backgrounds [32] and build on colleagues' experiences of improving diversity in research (section 5.3). Sample size is not inflated to account for clustering by therapist given little evidence of this in our previous trials [30, 47]

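### The working-memory hypothesis concerns effect modification, but the only working-memory analysis not labelled exploratory is a correlation with raw BDI-II change, which mixes moderation with prognosis and baseline severity

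*Protocol*

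**What the plan says.** The secondary mechanistic objective (section 4.4.2) is "To determine whether baseline working memory capacity is associated with treatment response at 26 weeks". Section 10.1.2 gives the hypothesis behind it: "If the WM hypothesis is correct, then EMDR will be more effective in those with lower WM capacity". The next sentence turns this into a prediction inside one arm: "So, we predict a negative relationship between WM capacity and baseline to post-treatment symptom reduction in the EMDR group".

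The named analysis follows and is two-sided. The variables it relates are given as "WM capacity (three continuous measures) and change in depressive symptoms on the BDI-II between baseline and 26 weeks". The sentence naming this analysis does not repeat the restriction to the EMDR group; that comes from the sentence before it.

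Section 10.1.2 also says that associations will be explored with suitable regression models, and that the team will "undertake exploratory analyses testing for an interaction between baseline WM (for each of the three measures) and treatment allocation". It adds: "Tests for interaction will be interpreted with caution given that they will be underpowered".

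Two other places matter. Section 10.1.1 handles differential effects by chronicity and severity through interaction terms with allocation, and its primary model adjusts 26-week BDI-II for baseline rather than analysing raw change. Table 2 (section 6.8) marks the WM tasks at baseline for all eligible participants, not for the intervention group only, so usual care will have the same WM data.

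**The concern.** That EMDR is more effective at lower WM is a statement about how the EMDR-versus-usual-care difference varies with WM. A correlation between WM and change among treated patients is a different quantity, made up of three parts:

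- moderation, which is what the hypothesis is about;
- prognosis, meaning any relation of WM to outcome that would be present under usual care as well;
- a baseline-severity component, because change contains baseline: if low WM goes with a higher baseline score, low WM also goes with a larger fall through regression to the mean.

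Only comparison with the randomised usual-care arm removes the second part, and only adjustment for baseline removes the third. As ranked, the analysis that cannot separate these parts is the one not called exploratory, and the analysis that can is discounted in advance. At stake is the mechanistic conclusion about WM, which could be supported, contradicted or missed for reasons unrelated to EMDR.

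**Working it through.** **The plan's own figures.** Section 5.8.4: 5.1/13.5 = 0.378. At 90% power and two-sided 5%, a t-based calculation gives 148.04, so 149 per group. Section 6.6.2: 380 × 0.75 = 285 analysable, about 142 per arm at 1:1. These reproduce. The protocol gives no power for the WM correlation or the WM interaction.

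**Inputs.** From section 5.8.4: SD at follow-up 13.5 and baseline-to-follow-up correlation 0.20. Assumed, because the documents do not give them: baseline BDI-II SD of 10; WM standardised; a WM-baseline correlation of -0.2 or -0.3; prognostic and moderating slopes in units of 0.1 × 13.5 = 1.35 or 0.2 × 13.5 = 2.7 BDI-II points per SD of WM; a 5% two-sided level for the WM tests. Reduction means baseline minus 26-week score. The hypothesis predicts a negative WM-reduction correlation.

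**SD of change.** √(10² + 13.5² − 2 × 0.20 × 10 × 13.5) = √228.25 = 15.1.

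**Rejection probability.** For a correlation r with n = 142: Φ(|atanh r| × √139 − 1.96), plus the small opposite tail.

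**No moderation, WM related only to baseline severity.** Covariance of WM with reduction = r_WB × (10 − 0.20 × 13.5) = 7.3 × r_WB.
- r_WB = -0.2: -1.46/15.1 = -0.097, about 21% rejection (22% by simulation).
- r_WB = -0.3: -2.19/15.1 = -0.145, about 41% (42% by simulation).

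These rejections are in the predicted direction. With r_WB from -0.1 to -0.3 and baseline SD from 8 to 13.5, the induced correlation runs from -0.04 to -0.19 and rejection from 7% to 62%.

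**No moderation, WM prognostic at 0.2 in both arms.** The slope adds 2.7² to the variance: √(228.25 + 7.29) = 15.35, and r = 2.7/15.35 = 0.176, about 55% rejection. If low WM means a worse course, r is positive and essentially all rejections go against the hypothesis. They support it falsely only if the prognosis runs the other way. Across prognostic WM-reduction correlations of 0.10, 0.15, 0.20 and 0.25, rejection is 22%, 43%, 67% and 85%.

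**Both artefacts together, no moderation, low WM meaning worse course.** Rejection in the predicted direction, as (WM-baseline correlation, prognosis):
- (-0.2, 0.1): 3.0%
- (-0.2, 0.2): 0.2%
- (-0.3, 0.2): 0.9%

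**True moderation of 0.2 (2.7 points per SD, EMDR arm only), WM unrelated to baseline.** For the interaction adjusted for baseline, residual SD = 13.5 × √0.96 = 13.23, SE = 13.23 × √(2/142) = 1.57, z = 2.7/1.57 = 1.72, and power = Φ(1.72 − 1.96) ≈ 40%. A common prognostic slope does not change this.

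| Opposing prognosis | Net slope in EMDR arm | Correlation rejects | Interaction rejects |
|---|---|---|---|
| 0 | 2.70 | about 55% | about 40% |
| 0.1 | 1.35 | about 19% | about 40% |
| 0.2 | 0 | about 5% | about 40% |

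**Error rate of the interaction with no moderation.** By simulation, 5.0% when WM is only prognostic and 4.7% when it is related only to baseline severity.

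**Interaction power.** Smallest r in EMDR, with 0 in usual care, for 80% power: tanh(2.80 × √(2/139)) ≈ 0.32. At r = 0.20 it is 39%.

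**The case against.** The strongest reply is that nothing is missing. The interaction is planned for each measure, its low power is disclosed, and the protocol says only that it will report a correlation; it names no lead analysis and no decision rule. All of that is correct, and a reader who inferred that the valid test had been left out would be wrong. What remains is a question of rank: the correlation is tied directly to whether the WM hypothesis is right, and the other WM analyses are described as exploring or exploratory.

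It is also fair that the test sentence does not itself limit the correlation to the EMDR arm. Pooling both arms would not help, because a pooled correlation still contains prognosis and baseline severity. The unspecified regression models might adjust for baseline, but a model in one arm cannot separate prognosis from response to treatment.

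A reader might take the 55% figure as the chance of falsely supporting the hypothesis. It is not. In the direction where low WM means a worse course, those rejections contradict the hypothesis. The baseline-severity artefact pushes the other way, and the two can largely cancel. Nor is the correlation always less likely to reject under true moderation: with no opposing prognosis it rejects more often than the interaction (about 55% against 40%). That is not an advantage in evidence, since it rejects about equally often under prognosis alone.

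Finally, the interaction is weak at this sample size. That stands.

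**Conclusion.** The point holds as a matter of ranking and inference for a secondary mechanistic objective. The correlation with raw change cannot be read as a test of whether EMDR works better at lower WM: a significant result may be prognosis or regression to the mean, and a null result may be moderation offset by opposing prognosis. The 5% rejection under true moderation is the exact-cancellation case; partial offset gives intermediate figures.

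All these rates depend on the assumed WM correlations and baseline SD, which the documents do not give. The structural argument does not depend on them. The documents do not support any claim that the trial is likely to report false support for the WM theory, because the sign and size of WM's prognostic relation are unknown.

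**What to change.** For the secondary mechanistic objective, state that inference on the WM hypothesis rests on the arm-by-WM interaction already planned: a linear model for 26-week BDI-II with allocation, WM and their product, adjusted for baseline BDI-II and the stratification and minimisation variables, fitted for each WM measure and reported as an estimate with a 95% CI. Label the EMDR-arm correlation as descriptive and show it beside the same correlation in usual care.

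The cost is wording in section 10.1.2 and the SAP; no new data are needed. The downside is a wide interval: power is about 40% for moderation of 0.2 SD per SD of WM and reaches 80% only near r = 0.32. The protocol already concedes this limitation, so the result should be presented as an estimate rather than as a pass-or-fail test.
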